1. BACKGROUND

Cytarabine is a standard chemotherapy agent used in the treatment of AML. Cytarabine is an antimetabolite, specifically a pyrimidine nucleoside analog that is converted inside cells to an active metabolite that ultimately results in inhibition of DNA synthesis. It is used in various doses and can be used alone or in combination with other chemotherapy agents for the treatment of AML. High doses of cytarabine, known as HiDAC (doses > 1000 mg/m² IV), are given in many different regimens. A standard AML consolidation regimen given after induction chemotherapy is HiDAC 1000-3000 mg/m² IV q12 hours on Days 1, 3, and 5. HiDAC can also be given daily as an induction chemotherapy regimen in AML as HiDAC IV q12h x 12 doses (Days 1-6). This dose schedule was not based on a pharmacologic basis but has been widely used. Common side effects of cytarabine are nausea and/or vomiting, bone marrow suppression and associated toxicities (such as infection), rash, and mucositis. Specific to high-dose cytarabine only, ocular and neurologic toxicity can occur and patients are monitored closely for these adverse effects. Patients are provided with eye drops during and after chemotherapy, and given tests to evaluate for cerebellar toxicity (such as signing their name prior to each dose).

1.1 Acute Myeloid Leukemia Cancer Therapy

Acute myeloid leukemia (AML) is a rare type of cancer (1.1% of all new cancer cases); AML affects 4.3 people per 100,000 men and women per year.⁶ Patients undergo treatment to induce a complete remission if fit to receive chemotherapy. Once complete remission is confirmed after induction chemotherapy, AML patients receive consolidation chemotherapy. A standard AML consolidation regimen is HiDAC (cytarabine 1000-3000 mg/m² IV q12h on Days 1, 3, 5 every 28 days) x 3-4 cycles in USA.⁷ Many institutions use HiDAC as consolidation chemotherapy or as a bridge to hematopoietic stem cell transplantation. Dosing of cytarabine varies for treatment of AML; for consolidation, some regimens may include cytarabine 100-200 mg/m² continuous IV infusion Days 1-5 given in combination with anthracycline or HiDAC alone for 3-4 cycles. For induction regimens, often HiDAC is incorporated into various regimens, including cytarabine \geq 1000 mg/m² IV q12h x 8-12 doses. Doses depend on age, renal function, performance status and institution/provider. Generally, patients over the age of 60 years receive cytarabine 1000 mg/m² for HiDAC consolidation.⁸ UF Health Shands Hospital routinely uses cytarabine 1000 mg/m² IV q12h on Days 1, 3, and 5 up to 4 cycles (if tolerated) for standard chemotherapy consolidation in older AML patients. Jaramillo et al recently published results from two European trials showing that a modified consolidation regimen of HiDAC on Days 1, 2 and 3 reduced the duration of neutropenia and number of blood product transfusions in younger AML patients compared to standard HiDAC consolidation on Days 1, 3 and 5 with no adverse effects on long-term outcomes.¹ Dumas et al subsequently published a retrospective study of centers in France showing that adult patients age 18 to 60 years old with de novo or secondary AML

[figure not shown]
treated with the condensed HiDAC regimen showed 3 days less of neutropenia compared to the standard HiDAC regimen without any negative effect on OS, relapse or non-relapse mortality.² After these two trials were published, the NCCN guidelines recommended HiDAC 123 for AML patients ages 60 and under as another consolidation option.⁹ Since European centers use a different induction strategy often with two induction courses before consolidation and with a different health care system, it is not clear if similar findings of safety and less health care utilization would be seen in US centers. Both published trials included only patients 60 years or younger. However, the median age at diagnosis of AML is 68 years old in the US.⁶ We will evaluate this abbreviated regimen and compare it to the standard of care regimen on Days 1, 3, and 5 in our older AML patient population, to try to reproduce the hematologic toxicity results seen in younger individuals using standard practices here in the US. We do not anticipate non-hematologic safety concerns since twice daily high dose cytarabine regimens are commonly used for patients who receive a second induction regimen if leukemia is not cleared by day 14 or at recovery after the first induction chemotherapy regimen and doses are routinely given for 6 continuous days rather than the 3 days of this regimen.¹⁰ Patients older than 50 years received cytarabine 2,000 mg/m² IV q12h D1-6 for induction chemotherapy, and this study only reported 7% severe neurotoxicity in this population.

In the proposed exploratory analysis, we will genotype patients for SNPs of relevance to cytarabine that can generate Ara-CTP SNP scores (ACSS as described in recent publication⁵). Given small sample size we will consider dividing patients into two groups (ACSS ≥ 0 and < 0) and will evaluate for association with toxicity and response to cytarabine that may be able to provide a model to identify patients who could be at higher risk for cytarabine toxicity. These SNPs are used in conjunction with next-generation sequencing (NGS) results to quantify the leukemia-associated variant allele frequencies. We hope to validate the clinical utility of ACSS to apply this score to explore if there is an association with relapse rate and risk of adverse effects in older adult AML patients undergoing HiDAC consolidation chemotherapy. This is an exploratory analysis to see if it is feasible to use this ACSS score and deep genetic sequencing to eventually be used in clinical practice and provide a patient-specific treatment plan. For example, we may be able to identify patients more at risk for adverse effects if he/she has high ACSS score and/or predict treatment failure in patients with low ACSS scores that could help guide different dosing strategies for dose optimization for individualized patients to decrease cytarabine toxicity without compromising cytarabine effectiveness. This approach could lead to the development of clinical research aimed at enhancing the adoption of best practices in the community if it is later evaluated in a larger population if we find this approach feasible.

1.2 Overview of Non-Clinical Studies

Cytarabine is a prodrug requiring activation to ara-CTP for its anti-leukemic effect. Intracellular levels of ara-CTP vary among AML patients and are critical for achieving significant leukemic cell death.⁵ One of the mechanisms underlying ara-C resistance is insufficient intracellular levels of ara-CTP, which may be due to: a) inefficient cellular uptake due to transporter levels; b) reduced activation due to alterations in enzymes as DCK, CMPK1; c) increased inactivation due to NT5C2, SAMDH1, CDA, or DCTD; d) increased cellular dCTP pools (regulated by ribonucleotide reductases), that can compete with DNA incorporation of ara-CTP and also inhibit DCK activity.

[name] group has previously reported association of SNPs in DCK, NT5C2 and RRM with intracellular levels of ara-CTP in leukemic cells.¹¹⁻¹³ Using the most informative SNPs within the ara-C metabolic pathway, we have recently developed a comprehensive Ara-CTP SNP score (ACSS) that is predictive of intracellular levels of ara-CTP within leukemic cells. See Figure 2. A comprehensive ara-CTP-SNP-score (ACSS) developed from top 4 SNPs classified patients into 3 groups: High-ACSS (score>0), Intermediate-ACSS (score=0) and Low-ACSS (score<0). ACSS designation significantly predicted with intracellular ara-CTP levels ($p=0.00012$), suggesting a cumulative or synergistic effect of the significant SNPs.⁵ More recently a study (unpublished results) with Moffitt Cancer Center, we observed significant correlation between induction 1 response being significantly ($p<0.0001$) better in patients with high ACSS score (≥ 0) vs low ACSS score (0). These results open up opportunities for the clinical utility of ACSS score to help identify patients who may be high risk of treatment failure or toxicity based on the ACSS scores.

1.3 Overview of Clinical Studies

For more detail refer to the prescribing information for cytarabine.¹⁴

Historically, poor outcomes were reported when conventional doses of cytarabine were used as post-remission therapy in AML, so groups studied higher doses of cytarabine for post-remission therapy. The Cancer and Leukemia Group B (CALGB) compared various doses of cytarabine consolidation in AML patients in CR after induction therapy.⁷ Subjects in this trial were randomized into three groups (each planned to receive 4 cycles of consolidation of the following): 1.) 100 mg/m² continuous IV x 5 days, 2.) 400 mg/m² IV daily x 5 days or 3.) 3000 mg/m² IV q12h x 6 doses on Days 1, 3, and 5. These authors found that subjects who received high dose cytarabine were more likely to remain in CR and lived longer than patients who received lower doses of cytarabine. This trial was pivotal in establishing HiDAC as the standard post-remission/consolidation chemotherapy in the USA, as it was the first to show superior efficacy outcomes compared to anthracycline and conventional dose cytarabine for consolidation. Hematologic toxicity was main adverse effect, and 71% of patients were hospitalized due to infection or febrile neutropenia. Growth factors were not used in the trial. After excluding subjects over the age of 60 years after seeing higher rates of CNS toxicity (32%), severe CNS toxicity was recorded in 12% of subjects aged 60 years or younger.

However more than half of patients are diagnosed over the age of 60 years with lower rates of CR compared to younger patients, so Sperr and colleagues designed a trial evaluating lower doses of cytarabine as consolidation chemotherapy in elderly AML subjects in CR.⁸ In this trial, patients received up to four cycles of cytarabine 1000 mg/m² IV q12h on Days 1, 3, and 5. Prophylactic growth factor was not routinely used. Neutropenic fever was recorded in 44-72% of cycles. No severe CNS adverse effects were reported. Drug fever was seen in 32% and rash occurred in 17% of cycles. The results of this trial demonstrated that elderly AML patients can tolerate attenuated doses of HiDAC, which became the standard consolidation regimen for many institutions in the US.

In 2006, the American Society of Clinical Oncology published guidelines that recommended prophylactic white blood cell growth factors after AML consolidation chemotherapy regimens. Bradley, et al published results of patients who did or did not receive prophylactic growth factor after first cycle of consolidation chemotherapy with at least 1000 mg/m² cytarabine q12h D1, 3, 5.¹⁵ Patients who received granulocyte colony stimulating factor (GCSF) had less readmissions for febrile neutropenia vs patients who did not receive GCSF (14% vs 37%).

In general, the neutrophil nadir starts around Days 7-10 after HiDAC consolidation, and most patients start to recover neutrophils between Day 21 and 24, but hematologic recovery

depends on various factors, such as age, amount of prior treatments, prior antecedent hematologic disorder, etc. The use of GCSF has decreased the time to hematologic recovery. Sierra, et al showed median time to neutrophil recovery after HiDAC consolidation therapy to be 17 days if given GCSF.¹⁶ In Jaramillo, et al, the median time to neutrophil recovery after 1-3 HiDAC consolidation(s) was 21-22 days in HiDAC 135 cohort compared to 17-18 days for subjects in the HiDAC 123 arm. Dumas, et al reported a median time of neutrophil recovery of 14-16 days with HiDAC 123 compared to 17-19 days with HiDAC 135.²

1.4 Rationale for Regimen/Doses/Schedule

This condensed schedule described by Jaramillo¹ and Dumas² will lessen the duration of chemotherapy inpatient admission by three days if older patients tolerate this new regimen. The authors also showed this modified HiDAC consolidation regimen reduced the duration of neutropenia and number of blood product transfusions in younger AML patients, so the benefits of this abbreviated regimen may be even greater than just three days less hospitalization. Patients were given pegfilgrastim as primary prophylaxis to prevent febrile neutropenia, however in the Jaramillo trial it was given on Day 10 in patients receiving HiDAC 135 and Day 8 in patients receiving HiDAC 123; this is typically later than many institutions in the US, as it is typically given or started approximately 24 hours after chemotherapy ends. The timing of GCSF prophylaxis described by Dumas et al more closely resembles to what we do in our practice, and the median time to recovery of neutrophils was slightly shorter compared to the results recorded by Jaramillo and colleagues. However, even in the trial described by Dumas, they described practices different than at this institution. For example, patients were routinely admitted on Days 10-12 according to blood cell counts and patients were not given bacterial prophylaxis. These trials were performed in Europe, which induction chemotherapy and supportive care measures are different than institutions in the US. Additionally, since AML patients are typically over 60 years with the median age at diagnosis of 68 years old⁶, we would like to study this patient population to potentially reproduce these reported results similar to the above trials. By reproducing these results seen in the aforementioned trials, it would make the benefits more generalizable to the AML population, especially to other institutions in the USA.

2. OBJECTIVES

2.1 Primary

2.1.1 Primary objective

- To determine the duration of neutropenia in older patients with de novo AML after consolidation chemotherapy with HiDAC 123 compared to historical controls with HiDAC 135. We expect to see a shorter duration of neutropenia in subjects who receive HiDAC 123 compared to subjects who received HiDAC 135.

2.1.2 Primary endpoint

- To determine duration of neutropenia after HiDAC123 compared to HiDAC 135. Duration of neutropenia is defined as the number of days between first absolute neutrophil count (ANC) < 500 after chemotherapy to day of recovery, defined as first day when ANC > 500 for two consecutive days.

2.2 Secondary

2.2.1 Secondary objectives

- To define duration of thrombocytopenia in older patients with de novo AML after consolidation chemotherapy with HiDAC 123 compared to historical controls with HiDAC 135.
- To determine the safety of HiDAC 123 compared to standard HiDAC 135 in case controls

2.2.2 Secondary endpoint(s)

- To determine the safety of HiDAC 123 compared to standard HiDAC 135 in case controls by evaluating the differences in:
 - duration of neutropenia and thrombocytopenia (see neutropenia definition above). Thrombocytopenia is defined as the interval between the first day of platelets < 50x10³/uL after consolidation chemotherapy to the first day of recovery (defined as first day of platelets > 20x10³/uL if consecutive x 2 and not transfused)
 - incidence of documented infections (bloodstream infection (BSI), pneumonia, invasive fungal infection (IFI), Clostridium difficile infection (CDI), typhlitis, (see Appendix A) and rates of febrile neutropenia (defined as temperature \geq 38.3 C° once or \geq 38 C° for more than 1 hour and ANC less than 500/mm³ or expected to fall below 500/mm³ in next 48 hours)
 - number of RBC and platelet transfusions given per cycle will be recorded in units
 - readmission rates (incidence and reason for admission) and LOS recorded in days (total, including chemotherapy administration, and readmission days)
 - non-hematologic toxicity: focus on CNS/cerebellar and ocular as these are specific to high dose cytarabine, but will record incidences of any other grade 3-5 organ systems according to CTCAE v5 criteria
 - time to next treatment (next chemotherapy cycle, transplant, etc.; if chemotherapy was discontinued prior to planned date, what was the reason)

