Objectives:	
Primary:
 
 • To determine the duration of neutropenia after consolidation chemotherapy with HiDAC 123 compared to matched historical controls who received HiDAC 135. Neutropenia is defined in days, as the first day of absolute neutrophil count (ANC) < 500 after chemotherapy to day of recovery [ANC > 500 (defined as first day above 500 if consecutive x 2)]. 
Secondary:
 
 • To define duration of thrombocytopenia after consolidation chemotherapy with HiDAC 123 compared to matched historical controls who received HiDAC 135. Thrombocytopenia is defined as the interval between the first day of platelets <50x10³/uL after consolidation chemotherapy to the first day of recovery (defined as first day of platelets >20x10³/uL if consecutive x 2 and not transfused). • To determine the safety of HiDAC 123 compared to standard HiDAC 135 in case controls by evaluating the differences in: 
 ○ duration of neutropenia and thrombocytopenia ○ incidence of documented infections (e.g., bloodstream infection (BSI), pneumonia, invasive fungal infection (IFI), Clostridium difficile infection (CDI), typhlitis, (see Appendix A) and rates of febrile neutropenia (defined as temperature \geq 38.3 C° once or \geq 38 C° for more than 1 hour and ANC less than 500/mm³ or expected to fall below 500/mm³ in next 48 hours) ○ number of RBC and platelet transfusions given per cycle will be recorded in units ○ readmission rates (incidence and reason for admission) and LOS recorded in days (total, including chemotherapy administration, and readmission days) ○ non-hematologic toxicity: focus on CNS/cerebellar and ocular as these are specific to high dose cytarabine, but will record incidences of any other grade 3-5 organ systems according to CTCAE v5 criteria.³

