Exclusion Criteria:	
Subjects with any of the following will not be eligible for study participation:
 
 A. Age < 61 years B. Patients unable to provide informed consent for prospective arm C. Secondary AML (documented history of antecedent hematological disorder, such as myelodysplastic syndrome or therapy-related AML) or CML in blast crisis D. Patients receiving, received, or who will receive a FLT3 inhibitor E. Patients receiving, received, or who will receive an IDH1 or IDH2 inhibitor F. SCr greater than 2 mg/dL G. Karnofsky PS of 40 or less at study entry H. History of any other disease, metabolic dysfunction, physical examination finding, or clinical laboratory finding giving reasonable suspicion of a disease or condition that contraindicates the use of protocol therapy or that might affect the interpretation of the results of the study or that puts the subject at high risk for treatment complications, in the opinion of the treating physician I. Prisoners or subjects who are involuntarily incarcerated, or subjects who are compulsorily detained for treatment of either a psychiatric or physical illness J. For historical arm, subjects will be excluded if adequate data is not available in electronic medical record (e.g., if patient was followed by their local oncologist between chemotherapy cycles and labs/transfusions/clinic notes, etc. are not available)

Efficacy Assessments:	
Duration of neutropenia after consolidation chemotherapy is primary efficacy endpoint. Neutropenia is defined in days, as the interval between the first recorded day of ANC < 500 after chemotherapy started to recovery [ANC > 500 (recorded as first day above 500 if consecutive x 2)]. Primary analysis will be with first consolidation cycle; however, data will be collected for all consolidation cycles up to six months after starting consolidation.
 
Duration of thrombocytopenia will be a secondary efficacy endpoint. Thrombocytopenia is defined as interval between the first recorded day of platelets < 50x10³/uL after consolidation to recovery (recorded as first day of platelets > 20x10³/uL if consecutive x 2 and not transfused within the past 7 days). Analysis will be with first consolidation cycle; however, subjects will be monitored for up to six months after start of consolidation.

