3. STUDY DESIGN

3.1 Study Overview

This is a single center, open-label, non-randomized phase II study. Twenty nine (29) subjects are planned to be enrolled in this study. Each subject will be administered cytarabine 1000 mg/m² IV q12h x 6 doses on Days 1-3 in the hospital during the consolidation treatment phase. Subject may receive up to four consolidation cycles. Subjects will have laboratory and toxicity assessments as clinically indicated (at baseline, then daily while inpatient and ideally every 48 hours after hospital discharge +/- 24 hours until count recovery from each cycle). These subjects will be compared to 29 historical controls [matched by age (within 3 years), gender (male or female), PS (Karnofsky: 90-100, 70-80, or 50-60) and number of HiDAC cycles received] who received HiDAC 135 from the time period of 2/1/2017-2/1/2019.

Screening data will be reviewed to determine subject eligibility. Subjects who meet all inclusion criteria and none of the exclusion criteria and who have consented will be entered into the study. The following treatment regimen will be used for prospective arm: cytarabine 1000mg/m² IV q12h x 6 doses (Days 1-3) for up to four cycles.

Historical arm subjects will have received cytarabine 1000 mg/m² IV q12h x 6 doses (Days 1, 3, and 5) for up to four cycles from the time period of 2/1/2017-2/1/2019.

Total duration of subject participation will be up to six months from start of first consolidation cycle (each cycle is 28 days, but more time may be required allowing extra time for delayed count recovery in some patients); study participation will end when subject recovers neutrophils and platelets after last administered cycle of chemotherapy, is admitted for conditioning chemotherapy for HCT, dies, or withdraws consent (whichever comes first). However, subjects will be followed every 3 months (\pm 28 days) for up to 48 months after start of induction to determine long-term outcomes. Total duration of the study is expected to be 60 months.

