9.2 Correlative Studies

We will compare the ACSS score for association with clinical endpoints using appropriate statistical tests as used in our previous work. Statistical analysis will be performed to compare overall-survival (OS), between ACSS groups using Cox regression and Fisher's exact test for toxicity endpoints and Wilcoxon test for association of ACSS score with duration or neutropenia/thrombocytopenia.

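### Platelet counts between 20 and 50 on the way down meet both the opening and the closing rule for thrombocytopenia, and the transfusion condition is worded in two ways (minor)

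*Combined protocol and SAP*

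**What the plan says.** The duration of thrombocytopenia is defined in three places. Counts here are in units of 10³/uL.

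- **Section 2.2.2**: "Thrombocytopenia is defined as the interval between the first day of platelets < 50x10³/uL after consolidation chemotherapy", ending at recovery, "defined as first day of platelets > 20x10³/uL if consecutive x 2 and not transfused".
- **Synopsis, Objectives**: the same opening rule; recovery is "defined as first day of platelets >20x10³/uL if consecutive x 2 and not transfused".
- **Synopsis, Efficacy Assessments**: the same opening rule; recovery is "recorded as first day of platelets > 20x10³/uL if consecutive x 2 and not transfused within the past 7 days".

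The parallel neutropenia rule in Section 2.1.2 opens below an ANC of 500 and closes at recovery, "defined as first day when ANC > 500 for two consecutive days".

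Section 3.1 sets the lab schedule: "daily while inpatient and ideally every 48 hours after hospital discharge +/- 24 hours until count recovery from each cycle". Appendix B gives a routine platelet transfusion trigger of 10,000/uL or below for leukemia.

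The duration is used in the secondary group comparison (Section 12.4, exploratory in nature) and in the pharmacogenomic analysis, where Section 9.2 plans a "Wilcoxon test for association of ACSS score with duration or neutropenia/thrombocytopenia". Section 12.5 calls exploratory endpoints descriptive.

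**The concern.** The opening threshold (50) lies above the closing threshold (20), and no definition says that recovery must follow a fall to 20 or below. Every count between 20 and 50 therefore satisfies both thresholds. A patient whose platelets are still dropping can meet the closing rule on the day the interval opens.

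Separately, two definitions exclude transfused values without giving a window, while the third gives seven days. Two people scoring the same chart from different pages could record different durations.

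At stake is whether this secondary endpoint measures platelet recovery or partly reflects which days blood was drawn and which definition was followed. The historical cohort is scored from records, so a rule that has to be interpreted is harder to apply identically to both cohorts.

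**Working it through.** The plan states no expected duration, power or sample size for thrombocytopenia, so there is no figure to reproduce. The 81% power in Section 12.2 concerns neutropenia.

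**1. Do the two ends overlap?** Opening: count < 50. Closing: two consecutive counts > 20. Both hold for any two successive counts between 20 and 50. For neutropenia the cut-off is 500 at both ends (< 500 and > 500), so no value satisfies both.

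**2. Does another clause prevent it?** The transfusion condition does not: the routine trigger is 10 or below, so a patient passing from 50 to 20 would ordinarily be untransfused. Requiring closure after the opening day does not either: in the course below, the next pair (36, 28) closes on Day 9, giving 9 − 8 = 1 day.

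**3. Worked example (assumed patient).** Counts on Days 5 to 24: 140, 90, 60, 45, 36, 28, 19, 12, 9, 9, 11, 14, 18, 24, 33, 47, 62, 80, 100, 120. The two consecutive values are read as two successive draws. Transfusion is assumed at drawn counts of 10 or below, with no increment modelled. The condition without a window is read as applying to the day itself.

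| Labs | Opens | As written, no window | Recovery after first count ≤ 20, no window | Same, 7-day look-back |
|---|---|---|---|---|
| Daily | Day 8 (45) | Day 8 (45, 36): 0 days | Day 18 (24, 33): 10 days | Day 21 or 22: 13 or 14 days |
| 48 h, even days | Day 8 (45) | Day 8 (45, 28): 0 days | Day 18 (24, 47): 10 days | Day 22: 14 days |
| 48 h, odd days | Day 9 (36) | Day 19 (33, 62): 10 days | Day 19: 10 days | Day 21: 12 days |

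As written, the same patient scores 0 or 10 days according to the lab days alone. With recovery counted after the first count at or below 20, all three schedules give 10. With daily labs the last assumed transfusion is on Day 14, so the look-back gives 13 or 14 days, depending on whether the seventh day falls inside the window.

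**4. How far could the share vary?** Assume an exponential fall with halving time h days, a nadir below 20, labs every s days at random phase, and the two-draw reading. The fall from 50 to 20 takes log2(50/20) × h = 1.32h days. The share scored 0 is (1.32h − s)/s, limited to between 0 and 1.

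| Labs every | h = 1 | h = 2 | h = 3 | h = 4 |
|---|---|---|---|---|
| 1 day | 32% | 100% | 100% | 100% |
| 2 days | 0% | 32% | 98% | 100% |
| 3 days | 0% | 0% | 32% | 76% |

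The halving times are assumptions. The range runs from none to all, so the calculation shows that the event is possible and says nothing about how often it would occur.

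**5. Details left open.** If the two consecutive values mean two calendar days, as the neutropenia rule says, strictly 48-hourly labs contain no adjacent-day pair and no recovery date can be recorded. A patient whose nadir stays between 20 and 50 scores 0 under the present wording, and the plan does not say whether that is intended. These two items are missing detail rather than contradictions.

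**The case against.** The strongest reply is that recovery already means a rise after suppression. Section 1.3 describes a nadir followed by recovery. Sections 3.1 and 6.3 continue labs until counts recover, and Section 3.1 adds that "study participation will end when subject recovers neutrophils and platelets after last administered cycle of chemotherapy". Those statements make little sense if recovery can be reached while counts are falling, and nothing shows that anyone would record 0 days for a patient on the way to 12. This stands as to intent: the post-nadir order is very probably meant. It does not repair the definitions, which date recovery by threshold alone.

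It can also be said that the illustrations rest on one invented course and that daily labs apply only to inpatients, whereas much of the fall may occur after discharge. That is fair, and it is why no frequency is claimed. The even-day row shows that 48-hourly labs can produce the same result.

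The version history says that transfusion language was updated to match the data-capture system, so an operational rule may exist there. The form is not in the documents, and the current text still carries two wordings.

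A reader might infer that the comparison is biased towards one schedule. The documents do not support this: the rule is the same for both cohorts, and nothing shows that lab spacing differs between them. A reader might also infer that using different thresholds to open and close is itself an error. It is not; the 50 and 20 thresholds can stay once the order is stated.

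**Conclusion.** The rule is wrong as written, and the severity is minor. All three definitions let a falling count between 20 and 50 open and close the interval together, and they contradict each other on the transfusion condition. That much follows from the text and needs no assumption. The sizes shown (0 against 10 days; 10 against 13 or 14 days with daily labs) belong to one assumed platelet course with assumed transfusions, and how often such cases would arise cannot be known from the documents.

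The effect is confined to the secondary thrombocytopenia comparison and the ACSS association. A reader might extend the point to the primary endpoint, but the neutropenia rule uses a single cut-off and does not have this overlap; the primary test, sample size and stopping rule are unaffected.

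**What to change.** For endpoint scoring only, in Section 2.2.2 and in both synopsis definitions, and identically for both cohorts:

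1. Date recovery as the first day of the first qualifying pair of counts above 20 that comes after the first count at or below 20 in that cycle. This keeps the plan's first-day principle. Anchoring on the last count at or below 20 would not, because a single late dip would move a recovery that had already been sustained.
2. Use one transfusion look-back in all three places, and say whether its last day counts as inside the window.
3. While editing, state whether the two consecutive values are two draws or two calendar days and, if calendar days, how recovery is dated when draws are 48 hours or more apart.
4. State how a patient who never falls to 20 or below is scored. The wording in item 1 makes this necessary, because such a patient would otherwise have no recovery date.

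This removes the false 0 for any patient with a recorded count at or below 20. Some dependence on lab days remains. The cost is wording in three places before analysis; platelet counts and transfusions are already collected.

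### Total length of stay is used as a safety comparison although planned dosing days alone make it two days per cycle shorter for HiDAC 123

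*Combined protocol and SAP*

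**What the plan says.** The secondary objective in section 2.2.2, repeated in the synopsis, is "To determine the safety of HiDAC 123 compared to standard HiDAC 135 in case controls by evaluating the differences in" a list of items. One of these is readmission rates together with "LOS recorded in days (total, including chemotherapy administration, and readmission days". LOS is thus a safety measure, and the planned stay for giving the drug is counted in it.

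Section 3.1 sets the two schedules. Prospective subjects receive "cytarabine 1000 mg/m² IV q12h x 6 doses on Days 1-3 in the hospital during the consolidation treatment phase". For the controls, "Historical arm subjects will have received cytarabine 1000 mg/m² IV q12h x 6 doses (Days 1, 3, and 5") is the schedule. The number of cycles can be up to four in both cohorts and is a matching factor.

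Section 1.4 states that the condensed schedule "will lessen the duration of chemotherapy inpatient admission by three days if older patients tolerate this new regimen". The synopsis rationale also names a shorter stay among the hoped-for gains and says the group would like to adopt the regimen as standard if the published results are confirmed.

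Section 12.4 summarises secondary endpoints descriptively, with exploratory group comparisons and no named test. No section plans an LOS comparison that leaves out the planned administration days.

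**The concern.** A safety measure should show no difference when two regimens are equally toxic. Total LOS does not have that property here. The cohorts differ in planned inpatient days before any complication occurs, and the difference always favours HiDAC 123.

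Two things follow. An unchanged burden of complications would appear as a shorter stay in a list headed safety. And if HiDAC 123 prolonged the index admission, the extra days would first have to use up the built-in offset before mean total LOS looked worse. Prolongation of the index stay is the part most exposed, because no other listed endpoint counts it.

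**Working it through.** **Inputs.** From 3.1: six q12h doses on Days 1, 2 and 3, or on Days 1, 3 and 5; up to four cycles. From 1.4: a stated three-day reduction. From 12.2: 23 evaluable per group, 29 accrued. Not in the documents: the SD of LOS, and the time of discharge after the last dose. I assume an SD of 4 to 10 days, one inpatient stay per cycle in each cohort, and the same lag from last dose to discharge.

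**The plan's own figure.** The documents give no power for LOS. For the primary endpoint (3 days, SD 4, one-sided 5%, 23 per group), the noncentrality is 3 / (4 × √(2/23)) = 2.54. The noncentral t then gives 80.5% power, and the normal approximation 81.6%, against 81% stated. Accrual is 23 / 0.80 = 28.75, so 29. Both reproduce.

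**Built-in difference.** From first to last dose is 60 hours for HiDAC 123 and 108 hours for HiDAC 135, a gap of 48 hours. In calendar days this is 5 − 3 = 2 per cycle, or 2, 4, 6 and 8 days over one to four cycles. Matching on number of cycles keeps the offset at two days times the cycles received. With the figure in 1.4 the totals are 3, 6, 9 and 12 days; three days does not follow from the dosing days alone.

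**Masking.** If HiDAC 123 adds x unplanned days per cycle, the expected difference in total LOS (HiDAC 123 minus HiDAC 135) is x − 2. It is negative for every x below 2 and zero at x = 2.

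**Illustration of size.** Suppose there is no difference in unplanned days. The probability that a two-sided 5% equal-variance t-test is significant is P(|T| > t) for a noncentral T with 2n − 2 degrees of freedom and noncentrality shift / (SD × √(2/n)). For n = 23 and SD 4 the noncentrality is 2 / (4 × √(2/23)) = 1.70, the critical value is 2.015, and the probability is 38%.

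| Assumed SD of LOS (days) | 2-day shift, n = 23 | 2-day shift, n = 29 | 3-day shift, n = 23 | 3-day shift, n = 29 |
|---|---|---|---|---|
| 4 | 38% | 46% | 70% | 80% |
| 6 | 20% | 24% | 38% | 46% |
| 8 | 13% | 15% | 24% | 29% |
| 10 | 10% | 12% | 17% | 20% |

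Without a built-in shift each entry would be 5%. The t-test is my choice, since 12.4 names none. The offset in the means does not depend on the test or the SD.

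**The case against.** The strongest reply is that little rests on LOS. It is one secondary item, compared in an exploratory fashion (12.4). Safety data are descriptive (12.6), and the stopping rule uses neurological toxicity only (12.7). Nothing says that a shorter stay will be taken as proof of lower toxicity, and 1.4 announces the schedule-driven reduction openly. All of this stands, and it limits the point to one of labelling and tabulation. It does not remove the offset, because a descriptive mean carries it as much as a test does.

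A reader might infer that total LOS can hide extra unplanned days in general. The documents do not support that. Readmission incidence and reason, infections, febrile neutropenia, transfusions and grade 3-5 toxicity are each compared in 2.2.2. The wording can also be read as listing readmission days as their own item. What can stay hidden is mainly a longer index admission.

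A reader might also infer that readmission rates are biased against HiDAC 123, because a complication on Day 4 or 5 is a readmission in one cohort and part of the planned stay in the other. This is possible but minor. Section 1.3 places the start of the neutrophil nadir around Days 7-10, after dosing has ended in both cohorts, and no section says when patients are discharged.

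**Conclusion.** The point holds in a limited form. Total LOS, as defined, favours HiDAC 123 by two days per cycle at equal toxicity (three by section 1.4), so it cannot serve as a safety comparison. It remains a fair measure of resource use. The two-day figure follows from the dosing days and assumes only that discharge follows the last dose at the same interval in both cohorts. The percentages are illustrative, because they rest on an assumed SD.

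The primary endpoint, its power and its alpha are not affected. The documents do not support saying that the trial's safety assessment as a whole is compromised. The change is worth making because it is cheap and removes a bias of known direction.

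**What to change.** In 2.2.2, the matching synopsis text and 12.4:

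- Report three quantities separately per cycle: planned administration days, index-admission days beyond the planned stay, and readmission days. Define the end of the planned stay by the same rule in both cohorts, including any routine discharge day.
- Base the safety comparison on additional (non-planned) inpatient days per cycle, meaning the second and third quantities together. Count them over the same length of follow-up after the last scheduled dose in both cohorts. Starting the count at Day 3 or Day 5 without fixing an equal length would give the cohorts unequal time in which to accrue days.
- Add a sensitivity count over a common window from Day 1, after subtracting planned days. A hospital day on Day 4 or 5 is still classed differently by cohort, so agreement between the two counts is the useful check.
- Keep total LOS as a description of resource use.
- Reconcile the three-day reduction in 1.4 with the two-day difference in dosing days in 3.1.

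The cost is a few sentences and a small amount of extra tabulation. The counts need admission and discharge dates. The documents imply these, since LOS and readmission days cannot be computed without them, but do not list them as data items, so the case report form should be checked for both cohorts.
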